9.1.2. Exclusion Criteria

All patients meeting inclusion criteria will be included in the study; no exclusion criteria will be applied.

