9.3.2. Outcomes

When available, the following variables will be collected after initiation of Mysimba/Contrave (Post-Index Date). A draft listing of variables available in each country is included in Appendix 3 and will be included as final in the Statistical Analysis Plan (SAP).

Proprietary and Confidential:

This document cannot be used, distributed, or reproduced in any way without the prior written consent of Currax Pharmaceuticals LLC.

- 1. BMI, height, and weight prior to index date, the date of initiation of the medication(s) of interest, (obtained directly from data sources; BMI may be calculated if height and weight available). In the event that BMI and/or weight are not available through licensed access to the Scandinavian National Patient Registries, an attempt will be made to identify the obese population through diagnosis codes or procedures such as counseling for weight loss. It should be noted that this approach may identify a more obese and more motivated population than what would be identified on the basis of BMI. In addition, an approach may be implemented to predict BMI or apply published algorithms predicting BMI. Details will be laid out in the SAP.
- 2. Weight will be obtained if available 16-24 weeks post-index date to evaluate use inconsistent with labelled indication. BMI after index date will be obtained in the same timeframe, if available.
- 3. Relevant comorbidities (obtained via ICD-10 codes):
 - 1. Weight-related comorbidities (i.e., type 2 diabetes, dyslipidaemia, hypertension)
 - 2. Neuropsychiatric conditions (mania, bipolar disorder, major depressive disorder [MDD], anorexia nervosa, bulimia)
 - 3. Uncontrolled hypertension
 - 4. Moderate or severe renal impairment
 - 5. End-stage renal disease
 - 6. Seizure disorder
 - 7. Hepatic impairment (defined by Child-Pugh score category)
 - 8. Central nervous system tumour
- 4. Concomitant medication use, including: naltrexone, bupropion, CYP2B6 inhibitors, CYP2B6 inducers, CYP2B6 substrates, CYP2D6 substrates, drugs that lower seizure threshold, opioid or opiate agonist, or MAOI (obtained via ATC [outpatient, Nordic data] or NDC [US data])
- 5. Pregnancy status and breastfeeding status (obtained via ICD-10 codes)
- 6. AESIs (obtained via ICD-10 codes):
 - 1. Seizures

- 2. Suicidality (i.e., suicidal ideation, attempted suicide or completed suicide)
- 3. Neuropsychiatric events (i.e., mania or depression)
- 4. Hepatotoxicity
- 5. Severe hypersensitivity reaction

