- 6. Serotonin syndrome
- 7. Major adverse cardiovascular events (i.e., cardiovascular-related death, non-fatal myocardial infarction, or non-fatal stroke)

Deaths will also be described by treatment group, for those with vital status available.

- 7. Treatment discontinuation (assessed using ATC [outpatient, Nordic data] or NDC [US data])
- 8. Reason(s) for treatment discontinuation (obtained via ICD-10 codes in the 90 days prior to discontinuation)

All variables will be identified from the data sources via a pre-specified list of definitions (i.e., code lists; see Appendix 2). Occurrence of AESI based on diagnostic codes will be summarized for all patients, and for a subgroup of patients who do not adhere to conditions of the EU SmPC for the Scandinavian countries (adapted to local SmPC as needed) or to the FDA SmPC for the US. Such criteria include: not meeting appropriate criteria for the indication [obese (BMI \geq 30 kg/m²), or being overweight (BMI \geq 27 kg/m² to < 30 kg/m²) and having at least one weight-related co-morbidity (e.g., type 2 diabetes, controlled hypertension, or dyslipidemia) based on diagnostic codes. If BMI is not available, diagnostic and procedure codes for obesity and weight loss will be applied, recognizing that it will likely produce a more obese population than would be identified by BMI. Subgroup analyses will also be conducted to assess continuous treatment in patients with either renal or hepatic impairment.

Initiation of specific medications that could result with the occurrence of an event corresponding to an AESI (e.g., newly initiating anti-epileptic/seizure medication, newly initiating medications indicated for mania or depression) will also be tabulated. For hepatotoxicity, liver function tests can be used (when available) in addition to diagnostic codes.

For reason(s) patients who discontinue treatment (i.e., do not refill their prescription), events (potential AESIs and contraindications) and clinical status (magnitude of weight loss or gain)

Proprietary and Confidential:

occurring within the 90-day window prior to discontinuation will be summarized. It should be noted that weight may not be available in the Scandinavian registries.

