To allow for multiple cycles of Mysimba/Contrave use and assessment of outcomes after initial exposure, the follow-up window for data collection after the index date will be up to 548 days (18 months), as an appropriate time-horizon for this specific purpose. All patient time during the follow-up window will be captured and censoring will occur at the earliest of death, disenrollment, 548 days of follow-up, or end of the study period (December 31, 2023).

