9.3.3. Covariates

When available, the following variables needed to conduct analysis for the primary and secondary research objectives will be collected. Variable availability from each country will be summarized in the SAP and is included in Appendix 3 in draft form.

Demographics and Baseline variables (Within 365 days before index date unless otherwise stated below; as depicted in Figure 1):

- 9. Patient demographics (age and sex on index date) (obtained directly from data source)
- 10. BMI, height, weight (most recent value on or before the index date) (obtained directly from data sources; BMI may be calculated if height and weight available)
- 11. Relevant comorbidities (obtained via ICD-10 codes), including:
 - 1. Weight-related comorbidities (i.e, type 2 diabetes, dyslipidaemia, hypertension)
 - 2. Neuropsychiatric conditions (mania, bipolar disorder, major depressive disorder [MDD], anorexia nervosa, bulimia)
 - 3. Uncontrolled hypertension, if possible
 - 4. Moderate or severe renal impairment
 - 5. End-stage renal disease
 - 6. Seizure disorder
 - 7. Hepatic impairment (defined by Child-Pugh score category, if available)
 - 8. Central nervous system tumour

- 12. History of, or current substance abuse/dependencies including acute opiate withdrawal (obtained via ICD-10 codes)
- 13. History of uncontrolled hypertension, seizures, bipolar disorder, MDD, anorexia nervosa, or bulimia (obtained via ICD-10 codes)
- 14. Prior medication use, including: naltrexone, bupropion, CYP2B6 inhibitors, CYP2B6 inducers, CYP2B6 substrates, CYP2D6 substrates, Monoamine oxidase inhibitors, Opioids, Opium alkaloids and derivatives and drugs that lower seizure threshold (obtained via ATC [Nordic data] or NDC [US data]) see Appendix 2 and 2A
- 15. Pregnancy status and breastfeeding status (obtained via ICD-10 codes)

All variables will be identified from the data sources outlined below using a pre-specified list of definitions per database (Appendix 3), to be defined in the SAP as final.

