9.7.3. Incidence Rate of AESIs

The incidence rate of AESIs per person-years of exposure after initiation of Mysimba/Contrave will be assessed. Person-time of exposure will be calculated as the duration from the index date through the date of last Mysimba/Contrave prescription or dispensation (i.e., total treatment duration of Mysimba/Contrave), as applicable, plus 4 weeks. The number of cycles of Mysimba/Contrave during the exposure period will be summarized comparing all users, irrespective of their treatment duration status.

For each type of AESI, the crude incidence of new AESIs will be reported and the incidence proportion and 95% CI of will be estimated as the number of patients experiencing each type of event during Mysimba/Contrave exposure divided by the number of patients initiating treatment with Mysimba/Contrave. The proportion will be reported per 1,000 persons. The incidence density rate and 95% CI of AESI will be reported per 1,000 per person-years, using the sum of the person-years of the at-risk population as the denominator.

Further, clinical events of interest that might be associated with the occurrence of a potential AESI (e.g., newly initiating anti-epileptic/seizure medication, newly initiating medications indicated for mania or depression) will also be tabulated. For hepatotoxicity, liver function tests can be used (when available) in addition to diagnostic codes.

For reason(s) patients who discontinue treatment (i.e., do not refill their prescription), clinical events and health status occurring within the 90-day window prior to discontinuation will be summarized.

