9.7.3.1. Incidence Rates of AESIs in Subgroups of Patients

If data are available and appropriate predictors are available in the respective database, sensitivity analyses around the definition of each type of AESI will be performed. Incidence proportion and density of each type of AESI will also be calculated for the subgroup of patients compliant or non-compliant with the EU SmPC (as listed in section 9.7.1, the criteria will be adapted for the relevant country of the data source stems if the SmPC differ across such countries, i.e., for U.S.), including relevant comorbidities, concomitant medications, and pregnancy. Adaptations will be made if BMI is not available; these will be described in the SAP. The incidence rate (and 95% CI) of new onset comorbidities and concomitant medication after initiation of Mysimba/Contrave will be assessed. Incidence rates will be determined both for the person-years of time exposed to Mysimba/Contrave (i.e., while patient taking medication) after the index date as well as for all person time through 548 days after the index Mysimba/Contrave prescription.

The incidence rate (and 95% CI) of pregnancy and breastfeeding after the Mysimba/Contrave index date will be assessed among females initiating Mysimba/Contrave. These analyses will be conducted in data sources where the necessary variables are present.

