	2.1.4 Which hypothesis(-es) is (are) to be tested?				
	2.1.5 If applicable, that there is no a priori hypothesis?				8

Comments:

2.1.4. There are no a priori hypotheses. This is a descriptive study only.

Sect	tion 3: Study design	Yes	No	N/A	Section Number
3.1	Is the study design described? (e.g. cohort, case-control, cross-sectional, other design)	\boxtimes			9.1
3.2	Does the protocol specify whether the study is based on primary, secondary or combined data collection?				9.1, 9.2, 9.4, 9.7
3.3	Does the protocol specify measures of occurrence? (e.g., rate, risk, prevalence)	\boxtimes			9.7
3.4	Does the protocol specify measure(s) of association? (e.g. risk, odds ratio, excess risk, rate ratio, hazard ratio, risk/rate difference, number needed to harm (NNH))		\boxtimes		9.7
3.5	Does the protocol describe the approach for the collection and reporting of adverse events/adverse reactions? (e.g. adverse events that will not be collected in case of primary data collection)				9.7, 11

 $^{^{1}}$ Date from which information on the first study is first recorded in the study dataset or, in the case of secondary use of data, the date from which data extraction starts. 2 Date from which the analytical dataset is completely available.

$\overline{}$								
•	1	m	n	n	Δ	ni	ts	•
-	J				_		LJ.	

J.T IIIIS IS a descriptive study offi	3.4	This is a	descriptive	study	only	١.
---------------------------------------	-----	-----------	-------------	-------	------	----

3.5	This is	а	database	study	using/	deidentified	data.
-----	---------	---	----------	-------	--------	--------------	-------

Sect	tion 4: Source and study populations	Yes	No	N/A	Section Number
4.1	Is the source population described?	\boxtimes			9.1
4.2	Is the planned study population defined in terms of:				
	4.2.1 Study time period	\boxtimes			6, 9.1, 9.4
	4.2.2 Age and sex		\boxtimes		
	4.2.3 Country of origin	\boxtimes			9.1, 9.7
	4.2.4 Disease/indication	\boxtimes			7
	4.2.5 Duration of follow-up	\boxtimes			9.2-9.7
4.3	Does the protocol define how the study population will be sampled from the source population? (e.g. event or inclusion/exclusion criteria)	\boxtimes			9.1.1, 9.1.2

Comments:

4.2.2 All uses of Mysimba across all ages and sexes which meet the inclusion criteria in 9.1.1 will be included in the study

Sect	ion 5: Exposure definition and measurement	Yes	No	N/A	Section Number

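### The pregnancy rate is set among all female initiators, with no restriction to women of reproductive age, so it understates the rate among women who could conceive and varies with each country's age mix

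*Protocol*

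**What the plan says.** Section 9.7.3.1 of the protocol sets the analysis: "The incidence rate (and 95% CI) of pregnancy and breastfeeding after the Mysimba/Contrave index date will be assessed among females initiating Mysimba/Contrave". The data-analysis part of the synopsis gives the same population and speaks of recorded breastfeeding.

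Nothing elsewhere narrows that population by age. Section 9.1.2 says "All patients meeting inclusion criteria will be included in the study; no exclusion criteria will be applied", and the comment on item 4.2.2 of the ENCePP checklist (Appendix 1) says "All uses of Mysimba across all ages and sexes which meet the inclusion criteria in 9.1.1 will be included in the study".

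For AESIs, section 9.7.3 defines the incidence density "using the sum of the person-years of the at-risk population as the denominator". The pregnancy sentence has no such wording.

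Section 9.3.2 lists the post-index variable as "Pregnancy status and breastfeeding status (obtained via ICD-10 codes"). Section 9.3.3 lists the same variable at baseline, where the window is "Within 365 days before index date unless otherwise stated below". Age and sex at index are also baseline variables. Appendix 3 rates pregnancy capture as available in the US and limited in the four Nordic sources, and breastfeeding capture as limited everywhere.

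**The concern.** An incidence rate is informative when the person-time in its denominator could have produced the event. Here the named population is every female who starts the drug. Women past childbearing age contribute follow-up but cannot contribute a pregnancy, so the result mixes two quantities: how often women who can conceive do so, and what share of female users they make up.

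The second quantity can differ between databases. Section 9.7.1 runs the analyses separately by country and then synthesises across the Nordic sources. Section 9.4.1 notes that reimbursement is restricted to the morbidly obese in Norway and Finland and absent in Sweden and Denmark, so the user populations may not be alike. A difference in the crude all-female rate could then reflect age mix alone.

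Breastfeeding has a related problem. It presupposes a delivery, so a rate over all female person-time mostly tracks how many women delivered.

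**Working it through.** The protocol states no expected pregnancy rate, count or age distribution, so there is no planned figure to reproduce. The check is algebra, with assumed inputs labelled as such.

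**Inputs from the protocol.** Population: all female initiators (9.7.3.1, synopsis). Age limit: none (9.1.2, Appendix 1 item 4.2.2). At-risk denominator: stated for AESIs only (9.7.3).

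**Input not in the protocol.** f, the share of female person-time contributed by women of reproductive age.

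**Step 1: dilution.** Let E be the number of pregnancies, PY the person-years of all female initiators, and f × PY the person-years of those of reproductive age. Essentially all of E arises in the second group.

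- Rate as written = E / PY
- Rate in women of reproductive age = E / (f × PY)
- Ratio of the first to the second = f, so the rate as written is lower by 1 − f

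| Assumed f | Rate as written is lower by | Restricted rate ÷ rate as written |
|---|---|---|
| 0.9 | 10% | 1.11 |
| 0.7 | 30% | 1.43 |
| 0.5 | 50% | 2.00 |
| 0.4 | 60% | 2.50 |

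The direction is certain if the sentence is followed literally. The size is not, because f is unknown.

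**Step 2: comparison between countries.** Suppose two countries share the same rate R among women of reproductive age, with f = 0.7 in one and f = 0.5 in the other (both assumed). The reported rates are 0.7R and 0.5R. Their ratio is 0.5 / 0.7 = 0.71, an apparent 29% difference produced by age mix alone.

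**Step 3: breastfeeding.** Over all female person-time, and counting women whose delivery is recorded, the rate equals (women with a delivery per person-year) × (share of them with recorded breastfeeding). Only the second factor concerns breastfeeding. A woman breastfeeding after index may have delivered before it, so the base for a proportion must include deliveries on both sides of index.

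**The case against.** The strongest reply is that this is a descriptive output. Pregnancy and breastfeeding are in none of the numbered objectives and are not AESIs. The study has no a priori hypotheses, and a rate per female user is a valid crude quantity. Age is described in each country, so a reader can see the mix. All of that stands, and it is why the all-female rate may be kept as a secondary figure. It does not remove the point: the protocol names the population itself, and a described age distribution does not let a reader recover the rate in women who could conceive.

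A second reply is that at-risk rules belong in the SAP, which is not shown. That holds for derivation detail, but the population here is written into the protocol twice. The reply also rightly notes that section 9.1.2 governs entry to the cohort. It shows that no age limit applies, but it does not prove that women pregnant at index count as at risk of a new pregnancy.

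A reader might go further and infer that pregnancies are dated by their first ICD-10 code, so that conceptions before index are counted as new. The documents do not support this. Section 9.3.2 names ICD-10 codes as the source and gives no dating rule, and section 9.3.3 collects pregnancy status before index, so pregnancies already coded can be separated. Dating of conception and overlap with exposure are ordinary SAP matters. Even under a simple model with a constant conception rate, one fixed coding lag and full follow-up, the pregnancies wrongly counted at the start equal in number those missed at the end, so the count does not shift.

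**Conclusion.** The point holds as a weakness in a stated analysis population. Followed literally, section 9.7.3.1 gives a pregnancy rate lower than the rate among women able to conceive, and one that moves with each country's age mix. The shortfall is 1 − f: 30-50% if 30-50% of female person-time is outside reproductive age. That range is an assumption, and the documents allow no estimate. Breastfeeding over all female person-time is hard to interpret rather than meaningless. No finding is made about how pregnancies are dated or whether conceptions before index are counted. Because the output is descriptive and tied to no objective, this is a worthwhile and inexpensive improvement and does not threaten the study's main results.

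**What to change.** In section 9.7.3.1 and the synopsis:

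1. Define the pregnancy rate per person-year among female initiators of reproductive age, for example 15-49 years at index, with no pregnancy recorded as ongoing at index. Keep the all-female rate as a secondary figure if wanted.
2. Report women pregnant at initiation separately, as a number and proportion, from the baseline pregnancy variable in section 9.3.3.
3. Report recorded breastfeeding as a number and proportion among women with a recorded delivery, before or after index, in place of a rate over all female person-time.

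**Cost.** Age, sex and baseline pregnancy are already collected, so items 1 and 2 need only wording and derivation code. Delivery is not a listed variable in section 9.3.2 or 9.3.3, so item 3 needs it derived where the source allows. The denominator shrinks and the confidence interval widens. For the age restriction alone, both limits scale with the rate by 1/f (1.43 at f = 0.7, 2.00 at f = 0.5, both assumed). Any events removed because the pregnancy was ongoing at index reduce precision further.

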9.7.4. Titration, Change in Dose, and Discontinuation

Among patients with available information, the proportion of patients with titration and dosing changes in alignment with the EU SmPC will be calculated. The local SmPC for the country of the data source may be used, if different than the EU SmPC.

Because reason discontinuation is rarely found in real world data, clinical events of interest and health status occurring within the 90-day window prior to discontinuation will be summarized for patients who discontinue treatment (i.e., do not refill their prescription). However, attribution to product is not possible.

9.7.5. Missing Data

For each database, the number and proportion of patients with missing values for important variables (i.e., patient demographics, history, comorbidities and conditions, or medication) will be reported. If missing values occur in >5% of patients within a database, then each missing data element will be imputed based on the mode of each variable within strata defined by BMI category, age, and sex. In this DUS study, characteristics of individuals with missing information on BMI and weight will be described separately, along with correlates of this missing information. BMI and weight will not be imputed in the primary analysis. Imputed variables will not be used when determining *use inconsistent with labelled indication*.

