9.9. Limitations on the Research Methods

9.9.1. EHR and Administrative Claims Data

The measurement of exposure to Mysimba/Contrave in EHR relies on the presence of a prescription for a medication while the exposure in administrative claims data relies on the presence of filled claims for the medication. For these reasons, certain data may not be captured because (a) treatment with Mysimba/Contrave is initiated and managed outside of the nationally reimbursed health system or (b) patients prescribed with Mysimba/Contrave do not take the medication. This may result in the extent of exposure being understated or overstated in the measures based on the duration of exposure used in the analysis.

Key variables such as weight, height, and BMI would not typically be available in administrative claims data. However, due to use of EHR and registers linked to EHR, these key variables are much more likely to be available. Height can be carried forward over an extended period, if needed. Weight is typically present at each clinic visit, which is where the medication would be prescribed, and thus starting weight is likely to be present. In the small number of instances in which weight is not available during the 365 days before the index date, it will be predicted conditional on other baseline variables and previous weight information. A similar approach will be taken for BMI.

Diagnostic codes reflect diagnoses or events that typically result in or are noted during a medical encounter. Those that are not associated with a medical encounter may not be captured.

Assessment after index Mysimba/Contrave prescription will occur both during periods of known use and during the pre-defined exposure period of 548 days after the index prescription. This may lead to attribution of findings to the medication even during periods of non-use. Additionally, data from clinical practice exhibit more heterogeneity than is seen in clinical trials. Thus, the data in this study are likely to represent a broad variety of patient experiences. The experience of any one individual may not be represented by the averages of the patient population. In addition, subgroups may exhibit different experiences than the overall population

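### Mode imputation within BMI strata distorts percentages for variables that can be missing, has no stratum for patients without BMI, leaves contraindications exposed, and conflicts with section 9.9.1 on weight and BMI

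*Protocol*

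**What the plan says.** Section 9.7.5 (Missing Data) first provides for a count of missing data in each database: "missing values for important variables (i.e., patient demographics, history, comorbidities and conditions, or medication) will be reported". It next sets a trigger for imputation, "If missing values occur in >5% of patients within a database", and gives no upper limit on missingness. The rule that applies once the trigger is met reads: "each missing data element will be imputed based on the mode of each variable within strata defined by BMI category, age, and sex".

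The same paragraph exempts two variables: "BMI and weight will not be imputed in the primary analysis". It ends by keeping imputed variables out of the determination of use inconsistent with the labelled indication. Contraindications are not mentioned, although section 9.7.2 lists them as a separate group (b) beside the indication group (a).

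Section 9.9.1 (EHR and Administrative Claims Data) says of weight missing in the 365 days before index that "it will be predicted conditional on other baseline variables and previous weight information". For the other measure it adds: "A similar approach will be taken for BMI". It describes these cases as few. Section 9.3.2 says instead that a BMI prediction approach may be used, with details in the SAP.

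On availability, Appendix 3 gives BMI, height and weight as *Partial* for the US and shows no availability for Denmark, Norway, Sweden or Finland. Section 9.3.2 agrees: "It should be noted that weight may not be available in the Scandinavian registries".

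**The concern.** The primary objectives are descriptive: baseline characteristics, and the number and percentage of patients compliant and non-compliant with the SmPC. Filling with the mode does not estimate the missing value. It assigns the commonest one to every patient in the stratum and then counts it as observed. For an uncommon contraindication, this turns not known into not present, and in a utilisation and safety study that is the direction that hides contraindicated use.

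The rule also needs BMI category to form its strata, while BMI is among the variables least available in these sources. Finally, two sections give different instructions for missing weight and BMI, so two analysts could both follow the protocol and produce different tables.

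**Working it through.** Section 9.7.5 states no numerical result, so there is no plan figure to reproduce.

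**Inputs**
- Rule and 5% trigger: section 9.7.5.
- n = 3,000 per database: section 9.5.
- p = 13.7%: a proportion quoted in section 9.5 for an adverse event, borrowed only as a convenient value. It is not a baseline prevalence from the protocol. p = 5% and p = 60% are assumed.
- Missing fraction m from 6% (just above the trigger) to 20%: assumed, because the protocol gives none. Missingness is taken as unrelated to the condition.

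**Expected estimate for a yes/no variable in one stratum**
- If p < 50%, the mode is absent and the estimate is p(1 − m).
- If p > 50%, the mode is present and the estimate is p + m(1 − p).

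| True p | m = 6% | m = 10% | m = 20% |
|---|---|---|---|
| 13.7% | 0.137 × 0.94 = 12.9% | 0.137 × 0.90 = 12.3% | 0.137 × 0.80 = 11.0% |
| 5% | 4.7% | 4.5% | 4.0% |
| 60% | 0.60 + 0.06 × 0.40 = 62.4% | 64.0% | 68.0% |

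Below 50%, the relative downward bias equals m. In patients, for n = 3,000, p = 5% and m = 20%: 150 true cases are reported as 120.

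**Interval width** (p = 13.7%, m = 20%)
- Filled values counted as observed: 1.96 × √(0.1096 × 0.8904 / 3,000) = 1.12 percentage points.
- Observed patients only (n = 2,400): 1.96 × √(0.137 × 0.863 / 2,400) = 1.38 percentage points.

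The interval is narrower than the data support and is centred on the wrong value.

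**Coverage of the nominal 95% interval** (simulation, n = 3,000, 20,000 replicates)

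| True p | m | Mode imputation | Observed values only |
|---|---|---|---|
| 13.7% | 6% | 72% | 95% |
| 13.7% | 10% | 38% | 95% |
| 13.7% | 20% | 0.3% | 95% |
| 5% | 6% | 86% | 95% |
| 5% | 10% | 71% | 95% |
| 5% | 20% | 22% | 95% |

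Most of this loss comes from the bias, not from the width.

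**Which variables can be missing.** Sections 9.3.2 and 9.3.3 take comorbidities from ICD-10 codes and medication from ATC or NDC codes. With such variables no code normally means absent, so the rule has nothing to fill. Measurement-based items differ. Appendix 2 defines uncontrolled hypertension by a code together with a systolic or diastolic threshold. Sections 9.3.2 and 9.3.3 define hepatic impairment by Child-Pugh category, which Appendix 3 lists as *Maybe* for the US and shows no availability for elsewhere. Uncontrolled hypertension and severe hepatic impairment are both contraindications in section 9.7.2.

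**Stratum.** BMI category is required, BMI is not imputed in the primary analysis, and section 9.7.5 gives neither a category for unknown BMI nor a fallback to age and sex.

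**Weight and BMI.** Section 9.7.5 says not imputed in the primary analysis. Section 9.9.1 says predicted, with no analysis named. Section 9.3.2 says BMI prediction is optional. These three statements are not one rule.

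**The case against.** The strongest reply is about scope. Most variables here are code-based, age and sex are available in all five sources, and BMI and weight are exempt in the primary analysis, so little may be left to impute. Appendix 3 even lists uncontrolled hypertension as available everywhere. This stands in large part and is why the point is limited to formally missing variables. It does not rescue the rule: section 9.7.5 itself names history, comorbidities, conditions and medication as variables that may be missing, and the measurement-based contraindications remain.

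Second, a reader might infer that all prevalences are pushed down. They are not: above 50% in a stratum the bias is upward.

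Third, a reader might infer that the weight and BMI conflict decides who enters the labelled-indication analysis. The documents do not support that. If predicted BMI counts as imputed, which is the natural reading, the last sentence of section 9.7.5 keeps it out of that classification.

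Fourth, a reader might infer that the rule cannot be run at all where BMI is absent. Section 9.3.2 provides substitute obesity diagnosis and procedure codes, section 9.7.3.1 promises SAP adaptations for the AESI subgroup analyses, and section 9.7.5 describes patients with missing BMI separately. None of these is tied to the imputation strata, so what stands is an undefined stratum with no stated fallback.

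Fifth, the words limiting the BMI exemption to the primary analysis leave room to read section 9.9.1 as a sensitivity analysis. That is possible, but section 9.9.1 does not say it.

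**Conclusion.** The concern holds in this limited form. The protocol fixes a single-imputation rule that is biased by construction for yes/no variables: downward by the missing fraction below 50% prevalence, upward above it, with intervals too narrow in both cases. At an assumed true value of 13.7%, the loss is about 0.8 percentage points at 6% missing (13.7 − 12.9), 1.4 at 10% and 2.7 at 20%. These sizes rest on assumed missing fractions and on missingness unrelated to the condition. The number of variables affected is probably small, but it includes contraindications, which the safeguard does not cover, so contraindicated use could be understated. The stratum for patients without BMI is undefined, and sections 9.7.5 and 9.9.1 conflict as written. This is a rule stated wrongly in the protocol and not a detail left to the SAP. It should be changed.

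**What to change.** 1. Delete mode imputation from section 9.7.5. In descriptive and compliance tables, report observed values with the denominator used and the number missing. Section 9.7.2 already counts missing data for categorical variables. This also removes the need for a BMI stratum.
2. Extend the sentence that keeps imputed variables out of the labelled-indication classification so that it also covers contraindications.
3. Keep BMI and weight unimputed in the primary analysis, label the prediction in section 9.9.1 as a sensitivity analysis, and align section 9.3.2 with it.

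Multiple imputation for adjusted AESI estimates is not needed, because the protocol plans no such estimates.

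The cost is a few sentences of wording and smaller denominators in some tables. Observed-only percentages still assume that missingness is unrelated to the condition, and the numbers missing let the reader judge that.
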